2.4.2 Known Potential Benefits

Successful decolonization with retapamulin may prevent future MRSA infections in subjects and transmission to family members. The findings will also advance our understanding of the efficacy of retapamulin as a novel decolonization strategy for mupirocin-resistant MRSA. If efficacious, this therapy will have a significant clinical impact upon general practice for control of MRSA colonization and infections within this outbreak community. This is especially important in the study group and strain we are investigating as it has been found to be resistant to the standard of care for decolonization.

3 Objectives and Purpose

3.1 Primary Objective

To assess the efficacy of retapamulin to reduce carriage of MRSA via a randomized, double-blind, placebo-controlled clinical trial testing retapamulin among pediatric patients with confirmed mupirocin-resistant nasal and/or rectal MRSA colonization. This study will investigate the efficacy of retapamulin to reduce MRSA colonization 1 week post therapy by 60% compared to placebo, assuming a 15% spontaneous decolonization rate.

3.2 Secondary Objectives (if applicable)

To assess the efficacy of retapamulin to reduce MRSA colonization 4 weeks post therapy.

CONFIDENTIAL

This material is the property of the NYU School of Medicine and Langone Medical Center. Do not disclose or use except as authorized in writing by the study sponsor
Interventional Template Version: 28 APR 2017

4 Study Design and Endpoints

4.1 Description of Study Design

The proposed study will be a randomized, double-blind, placebo-controlled clinical trial. Subjects who are positive for mupirocin-resistant methicillin-resistant *Staphylococcus aureus* (MRSA) based on nasal or rectal culture will be recruited. They will be randomized into one of the two arms to the study – retapamulin or placebo. They will be advised to apply the study drug to the nares and peri-rectal area twice a day for 5 consecutive days. Nasal and rectal colonization of MRSA will be observed at pre-determined points within the study timeframe as described below via nasal and peri-rectal culture. The participants will be cultured before and after the interventional drug and a final culture to assess long-term decolonization status. The primary outcome measures are nasal and/or rectal MRSA carriage at 1 week and 4 weeks post decolonization with retapamulin.

The participants will be recruited from NYU Langone Medical Center, specifically from Hassenfeld Children's Hospital's general pediatric and pediatric intensive care units (PICU). Hassenfeld Children's Hospital at New York University Langone Health consists of 4 inpatient units totaling 109 beds within a larger 1069-bed tertiary care academic medical center. There are 33 beds in our general pediatric ward and 14 PICU beds. Patients admitted from zip codes that are classified as Orthodox-predominant neighborhoods in Brooklyn will be recruited. As described in the background, a reference identified neighborhoods in Brooklyn determined to be mainly Orthodox based on the number of Jewish establishments (synagogues, yeshivas, and kosher food retailers) in the area.^[12] A report will be generated daily through the Infection Prevention database that identifies patients admitted from these zip codes. These patients, regardless of reason for admission except as noted in exclusion criteria, will be recruited by the study team.

Participants will also be recruited from the ODA clinic on Park Avenue in Williamsburg Brooklyn. Study team members will be going to the clinic for scheduled visits where participants can be screened for inclusion into study. These participants will be referred by their pediatricians, the members of the clinic, or by word of mouth. Additionally, participants who are recruited at NYU Langone can come to the ODA clinic for follow up visits for ease to the participants.

4.2 Study Endpoints

4.2.1 Primary Study Endpoints

The primary endpoint is % change in nasal/rectal colonization of MRSA from baseline to 1 week after completion of decolonization protocol with retapamulin compared to placebo.

This endpoint is important to determine the short term efficacy of the study drug to decolonize patients with MRSA.

4.2.2 Secondary Study Endpoints

The secondary endpoint is % change in nasal/rectal colonization of MRSA from baseline to 4 weeks after completion of decolonization protocol with retapamulin compared to placebo.

This endpoint is important to determine the long term efficacy of the study drug to decolonize patients with MRSA.

4.2.3 Exploratory Endpoints

Exploratory endpoints include: efficacy of decolonization per body site (nasal versus rectal), adverse events related to retapamulin use, and MRSA infections while on study/decolonization protocol.

CONFIDENTIAL

This material is the property of the NYU School of Medicine and Langone Medical Center. Do not disclose or use except as authorized in writing by the study sponsor
Interventional Template Version: 28 APR 2017

5 Study Enrollment and Withdrawal

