8.2.2 Relationship to Study Agent

The clinician's assessment of an AE's relationship to study agent is part of the documentation process, but it is not a factor in determining what is or is not reported in the study. If there is any doubt as to whether a clinical observation is an AE, the event should be reported. All AEs must have their relationship to study agent assessed. In a clinical trial, the study product must always be suspect. To help assess, the following guidelines are used.

- **Related** – The AE is known to occur with the study agent, there is a reasonable possibility that the study agent caused the AE, or there is a temporal relationship between the study agent and event. Reasonable possibility means that there is evidence to suggest a causal relationship between the study agent and the AE.
- **Not Related** – There is not a reasonable possibility that the administration of the study agent caused the event, there is no temporal relationship between the study agent and event onset, or an alternate etiology has been established.

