8.3 Time Period and Frequency for Event Assessment and Follow-Up

The occurrence of an AE or SAE may come to the attention of study personnel during study visits and interviews of a study participant presenting for medical care, or upon review by a study monitor. All AEs including local and systemic reactions not meeting the criteria for SAEs will be captured on the appropriate RF. Information to be collected includes event description, time of onset, clinician's assessment of severity, relationship to study product (assessed only by those with the training and authority to make a diagnosis), and time of resolution/stabilization of the event. All AEs occurring while on

CONFIDENTIAL

This material is the property of the NYU School of Medicine and Langone Medical Center. Do not disclose or use except as authorized in writing by the study sponsor
Interventional Template Version: 28 APR 2017

study must be documented appropriately regardless of relationship. All AEs will be followed to adequate resolution.

Any medical condition that is present at the time that the participant is screened will be considered as baseline and not reported as an AE. However, if the study participant's condition deteriorates at any time during the study, it will be recorded as an AE. UPs will be recorded in the data collection system throughout the study.

Changes in the severity of an AE will be documented to allow an assessment of the duration of the event at each level of severity to be performed. AEs characterized as intermittent require documentation of onset and duration of each episode.

The PI will record all reportable events with start dates occurring any time after informed consent is obtained until 7 (for non-serious AEs) or 30 days (for SAEs) after the last day of study participation. At each study visit, the investigator will inquire about the occurrence of AE/SAEs since the last visit. Events will be followed for outcome information until resolution or stabilization.

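### The adverse event endpoint in 4.2.3 counts only retapamulin-related events, but the relatedness categories in 8.2.2 overlap, so the same event can be counted or left out

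*Combined protocol and SAP*

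**What the plan says.** Section 4.2.3 names three exploratory endpoints. The one for adverse events is "adverse events related to retapamulin use". It does not cite a definition of related; the only one in the document is in 8.2.2.

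Section 8.2.2 has two categories. An event is Related if it is known to occur with the agent, if "there is a reasonable possibility that the study agent caused the AE, or there is a temporal relationship between the study agent and event". It is Not Related if there is no reasonable possibility of causation, if "there is no temporal relationship between the study agent and event onset, or an alternate etiology has been established". The same section requires that "All AEs must have their relationship to study agent assessed", but says of that assessment that "it is not a factor in determining what is or is not reported in the study". Section 8.3 agrees: "All AEs including local and systemic reactions not meeting the criteria for SAEs will be captured".

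Four other places bear on the endpoint:

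- 8.1 treats adverse effects that are more than minimal as a study endpoint, with no relatedness condition.
- 8.6 bases the halting rule on events judged probably related, a grade that 8.2.2 does not contain.
- 10.4.4 (Safety Analyses) describes monitoring and notification only.
- 10.4.11 says that no exploratory analyses are planned.

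**The concern.** An endpoint restricted by causality is only as reliable as the causality rule. Here each category is a list of alternatives, and one fact from each list can be true of the same event. Two assessors who both follow the protocol could file one event differently, and the reported count would depend on which half of the rule each applied.

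There is also a design cost. The placebo arm shows which events occur at the background rate, with no individual causality judgement needed. An endpoint worded as related to retapamulin does not use that comparison, because no event in a child given petrolatum can be caused by retapamulin.

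What is at stake is the tolerability statement. Section 2.4.1 says the drug has not been widely evaluated on mucosal surfaces, and 5.3 says there are no current studies in children for this use, so that statement has some value even as an exploratory result.

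**Working it through.** The plan gives no figure to reproduce on this point. The check is a logical one on the wording of 8.2.2, followed by a search for a section that settles the matter elsewhere.

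**1. Facts used by the rule.** K = known to occur with the agent; R = reasonable possibility of causation; T = temporal relationship; A = alternate etiology established. Each is yes or no, giving 2 × 2 × 2 × 2 = 16 combinations.

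**2. Literal reading.** Related = K or R or T. Not Related = (no R) or (no T) or A.

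| Facts | Combinations | Related | Not Related |
|---|---|---|---|
| R and T, no A (K either way) | 2 | yes | no |
| None of K, R, T (A either way) | 2 | no | yes |
| All others | 16 − 2 − 2 = 12 | yes | yes |

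The plainest case is T with A: a cold caught during the five dosing days. It is Related because "there is a temporal relationship between the study agent and event", and Not Related under the clause "or an alternate etiology has been established".

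**3. More forgiving readings.**

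- Some combinations are barely coherent. Setting aside the 4 with K but not R leaves 12 − 4 = 8 overlapping out of 16 − 4 = 12. Setting aside also the 4 with R but not T leaves 8 − 4 = 4 out of 12 − 4 = 8.
- If the first two Not Related conditions must hold together, Not Related = (no R and no T) or A. That covers 8 combinations with A and 2 without, or 10. Two of these have none of K, R, T, so 10 − 2 = 8 of 16 overlap. Among the 8 coherent combinations, 3 still overlap, and all 3 have both T and A.
- If all three conditions must hold together, 1 of 16 overlaps (K and A, without R or T), and that one is barely coherent. This reading would nearly remove the overlap, but it turns the text's or into and, and it leaves an event with none of the four facts in neither category.

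These are counts of logical cases. They say nothing about how often each would occur.

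**4. Does another section settle it?** Section 8.2.2 states no precedence. Section 8.1 adds a severity criterion that is not reconciled with 4.2.3. Section 8.6 uses a grade outside the two-level scale. Sections 10.4.4 and 10.4.11 plan no comparison of adverse events by arm. So no.

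**5. Scale of the count, for illustration.** Section 2.4.1 gives local irritation in under 2% of patients. If that rate carried over to the nares and peri-rectal area (an assumption), fewer than 27 × 0.02 = 0.54 treated children would be expected to have it. One intercurrent illness filed one way or the other would be at least as large as that.

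**6. After the change.** Counting all events by arm requires no relatedness decision, so the ambiguous combinations fall from 12 of 16 to 0 of 16. No sample size or power figure changes.

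**The case against.** The strongest reply is that the document already limits the harm, and much of this stands. Every event is recorded and assessed whatever its relationship. Section 10.3 places side effects and safety variables in the dataset beside the blinded arm code, and 8.7 has the medical monitor review safety data on each arm. An all-events count by arm therefore remains possible. Section 8.2.2 also calls its definitions guidelines and says the product must always be suspect, which leans towards Related. The expected reaction, local irritation after application, is Related only, unless another cause is established. The ambiguity falls mainly on intercurrent illness.

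Several stronger readings are tempting and are not supported:

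- *That 4.2.3 holds the only adverse event endpoint.* Section 8.1 makes more-than-minimal effects an endpoint on its face, and 4.2.3 also lists MRSA infections on study; neither is filtered by relatedness.
- *That relatedness cannot be judged under the blind.* Section 8.2.2 asks about the study agent, and a blinded clinician can judge that in either arm. Only the word retapamulin in 4.2.3 removes the placebo count.
- *That one arm is favoured.* Assessors are blinded under 10.6.1, so an unclear rule produces mainly noise.
- *That the small sample measures the defect.* With no events in 27 children, the one-sided 95% upper bound is 1 − 0.05^(1/27) = 0.105. That figure comes from the sample size and would be the same under any endpoint definition.

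What the reply does not remove is the missing precedence rule or the absence of any planned comparison by arm. Data that could be tabulated are not the same as a specified analysis.

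**Conclusion.** The point holds as a wording and analysis-choice defect of low severity. The endpoint in 4.2.3 is filtered by a rule that can put one on-treatment event in both categories, and read literally it gives no control count. The overlap is present in 12 of 16 logical combinations as written. On the two readings that keep an or in the Not Related list, it persists for the ordinary case of an event during dosing with an established other cause.

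The conclusion assumes that 8.2.2 is the rule meant by 4.2.3, which is not stated, although no other definition exists. The likely number of misfiled events cannot be derived from the documents. A reader might infer that the count could swing from nearly all on-treatment events to almost none; that is a logical extreme, not a forecast. Data collection, sample size and both efficacy tests are unaffected.

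**What to change.** - **4.2.3 and 10.4.4:** define the safety endpoint as the number and proportion of children with any adverse event, and with any application-site event, by randomised arm and regardless of relatedness, with the difference and an exact 95% confidence interval. Keep relatedness to study agent as a descriptive listing.
- **10.4.11:** amend the statement that no exploratory analyses are planned so that it matches.
- **8.2.2:** make the two categories mutually exclusive by stating which governs when conditions from both lists are met.
- **8.1 and 8.6:** reconcile the severity-based endpoint wording in 8.1 with 4.2.3, and the probably related grade in 8.6 with the two-level scale in 8.2.2. Which wording should prevail is for the sponsor and investigator.

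The cost is protocol and SAP wording plus one table; the events are already to be collected. There is a small statistical cost: all-event counts include background illness, which dilutes the contrast for drug-caused events. The application-site count and the relatedness listing offset this.

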5.1 Inclusion Criteria

In order to be eligible to participate in this study, an individual must meet all of the following criteria:

1. Admission to the general pediatric floor and pediatric intensive care units at NYU Langone Medical Center or visit to study team members at ODA clinic (Park Ave locations) in Williamsburg Brooklyn.
2. Ages 9 months to 17 years
3. Residing in the zip codes which reflect Orthodox Jewish neighborhoods where there is a current outbreak of this strain of MRSA.
4. Nasal and/or rectal culture positive for mupirocin-resistant methicillin-resistant *Staphylococcus aureus* (MRSA)

5.2 Exclusion Criteria

An individual who meets any of the following criteria will be excluded from participation in this study:

1. Pregnant or lactating
2. Unable to appropriately consent
3. Open sores in either of the study sites (nares or rectum)
4. Recent surgical procedure to either study site (nares or rectum)
5. Concurrent use of Rifampin or Trimethoprim/Sulfamethoxazole
6. Current active MRSA infection
7. Immunocompromised
8. Presence of endotracheal tube, tracheostomy tube or other foreign body in upper airway

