2.4 Potential Risks & Benefits

2.4.1 Known Potential Risks

Known risks or adverse reactions from this drug use are minimal and include local application site irritation (pruritus, erythema, stinging). In clinical studies, this was found to occur in less than 2% of patients. Retapamulin has not yet been widely evaluated for use on mucosal surfaces. This information is listed in the package insert for retapamulin.

We do not anticipate that this research study will pose greater than minimal risk to participants. Side effects of Retapamulin not commonly expected and should subside with the discontinuation of the drug without expected long term risks. Serious side effects are rare and can include allergic reaction.

All efforts will be made to minimize risk for participants in this study. Study staff have been trained in human subjects' research and protection. The subjects will be instructed on proper use (amount, technique, duration) of the study drugs and potential effects to monitor for. If a side effect were to occur or there are any concerns, the subjects will be advised to call the research staff immediately and guidance or treatment will be offered as needed. Immediate necessary care for adverse events will be provided at NYULMC. Subjects will be monitored for side effects at each study visit and check-in via telephone to parent/guardian. If subjects experience serious adverse events or side effects to the study drug they will be withdrawn from the study.

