After informed consent, and assent when appropriate is obtained, screening nasal and peri-rectal cultures will be performed on these participants to determine if they are eligible to enroll. Eligibility includes either nasal or rectal positive for MRSA. Informed consent will take place either at NYULMC on the inpatient ward while they are admitted, at ODA clinic during time of screening, or at Fink Children's Ambulatory Center when present for a routine follow up visit. Participants will be asked to fill out a study questionnaire which asks about medical history, medication use, history of MRSA infections and prior use of antibiotics and specific MRSA medications. The study team will ask participants for this information via questionnaire only; it will not be gathered from their medical records. They study team will not access medical records or charts for participants.

The participants will be required to follow up at pre-defined time points throughout the 6 weeks study period to obtain follow up swabs, complete questionnaires regarding interim change in medical history or side effects experienced, and to collect containers from study drugs. Retention will be enhanced through telephone reminders of study visit appointments as well as payments for participation in the study. In addition, follow up for study visits for the participants recruited at NYULMC will occur at NYU Pediatric Infectious Diseases outpatient clinic as per routine medical management, at NYU Langone Main Campus, Greenberg Hall, or at ODA clinic (Park Ave location) in Brooklyn.

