8.1 Specification of Safety Parameters

Safety parameters and adverse reactions/side effects will be recorded in the participants chart in the study database. No more than minimal adverse effects (local application site irritation) are anticipated from using the study agent. If adverse effects are encountered by participants and considered to be more than minimal affect it would be considered a study endpoint and adverse effects should subside with withdrawal of study agent. If more than minimal adverse effect is experienced (eg anaphylaxis or allergic reaction) it will be reported to the industry partner and the IRB.

If subject develops MRSA active clinical infection while on study protocol, they will be cared for per routine medical management for such infections. This is anticipated to be rare. This development of disease while on protocol will be reported to the IRB and industry sponsor. If available, the isolates from these cases of active disease will be collected and analyzed by study team members and [name] laboratory to assess the bacterium and resistance determinants. Bacterial strain isolates will be stored. No material containing subject DNA will be collected or stored.

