8.6 Study Halting Rules

Administration of study agent will be halted when three grade 3 AEs determined to be "probably related" are reported to the DCC. In the case of this study agent, retapamulin, that would likely be serious allergic reaction or anaphylaxis. The DCC will notify the study sponsor and investigators immediately when the third grade 3 event is reported and enrollment screens will stop accepting new study participants. The study sponsor will inform the DSMB members within 24 hours of this occurrence and will provide the DSMB with AE listing reports. The DSMB will convene an ad hoc meeting by teleconference or in writing as soon as possible. The DSMB will provide recommendations for proceeding with the study to the study sponsor/NIH. The study sponsor will inform the FDA of the temporary halt and the disposition of the study.

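### Section 5.2 has no criterion for known hypersensitivity to a study ointment, and no described pre-dispensing step asks about allergy, although allergic reaction is the protocol's own example of a rare serious event

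*Combined protocol and SAP*

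**What the plan says.** **Eligibility.** Section 5.2 begins "An individual who meets any of the following criteria will be excluded from participation in this study". Its eight items cover pregnancy or lactation, inability to consent, open sores at the study sites, recent surgery there, rifampin or trimethoprim/sulfamethoxazole, active MRSA infection, immunocompromise and, last, "Presence of endotracheal tube, tracheostomy tube or other foreign body in upper airway". The four inclusion criteria in 5.1 cover care setting, age, zip code and culture result. Neither list mentions allergy or hypersensitivity.

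**Risk.** Section 2.4.1 states: "Serious side effects are rare and can include allergic reaction". Section 8.1 states: "If more than minimal adverse effect is experienced (eg anaphylaxis or allergic reaction) it will be reported to the industry partner and the IRB". Section 8.6, describing the events that would count toward halting, states: "In the case of this study agent, retapamulin, that would likely be serious allergic reaction or anaphylaxis". Section 10.6.3 gives anaphylaxis as its example of an event that allows a child's blind to be broken, and 10.4.4 and 10.4.5 also name it.

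**History taking.** Section 5.4 describes a questionnaire on medical history, medicines, MRSA infections and earlier antibiotic or MRSA treatment, and says of this information that "it will not be gathered from their medical records". Section 7.1.1 defines medical history as chronic conditions and past MRSA infections. Section 7.3.2 lists demographics and medical, medication and infection history at Visit 1. Allergies appear in none of the three.

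**The concern.** The protocol plans for an allergic event after it happens, through reporting, withdrawal, unblinding and halting. It does not say how a child already known to have reacted to one of the ointments is to be handled at entry. Section 2.4.1 undertakes to minimise risk as far as possible, and the participants are children who are dosed at home for five days.

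Earlier exposure is plausible. Section 2.2 says retapamulin has been approved since 2007 for impetigo and minor skin infections in patients over 9 months, and 10.3 plans to record prior retapamulin use. White petrolatum is both the vehicle of the active ointment and the placebo (6.1), so sensitivity to it would matter in either arm.

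The main stake is an avoidable reaction in a child. There is also a small cost in data. A child with a serious reaction is withdrawn (2.4.1), and a withdrawal before the 1-week swab is left out of the primary analysis (10.5).

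**Working it through.** This is a comparison of text. The plan gives no figure on this point to reproduce.

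1. **Could a known allergy make a child ineligible?** Allergy-related criteria: 0 of 8 exclusions (5.2) and 0 of 4 inclusions (5.1). As written, no.

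2. **Would a described step reveal it before dispensing?**

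| Step | Where | Allergy item described? |
|---|---|---|
| Questionnaire topics | 5.4 | No |
| Definition of medical and medication history | 7.1.1 | No |
| Screening steps | 7.3.1 | No |
| Visit 1 steps, including randomisation and dispensing | 7.3.2 | No |
| Schedule of events | 20 | No |
| Database variables | 10.3 | No; prior retapamulin use is the nearest |
| Medical records | 5.4 | Not accessed |

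   Allergies are listed in 0 of the 3 descriptions of the initial questionnaire (5.4, 7.1.1, 7.3.2). Prior use in 10.3 is not the same as a prior reaction, and 7.1.1 says medication use has no bearing on eligibility.

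3. **Does another provision close the gap?** Section 5.7.1 lets an investigator end participation for a medical condition, or because an exclusion criterion is met. The first ground is discretionary and applies to children already in the study. The second depends on the list in 5.2, which has no allergy item. Section 7.5.1 says no medication precautions are known for the agent, so it adds no check.

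4. **Compare with the risk sections.** Sections 2.4.1, 8.1, 8.6 and 10.6.3 each name allergic reaction or anaphylaxis. The eligibility and history sections are silent on it. The two groups of sections have not been aligned.

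5. **Data consequence.** Section 5.6 plans 54 enrolled to give 44 evaluable, an allowance of 54 − 44 = 10 losses. A child withdrawn early after a serious reaction would be one of those ten. This does not call for a different sample size.

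**The case against.** **The form itself was not available.** Section 19 lists the initial questionnaire, data collection form and package insert as separate attachments. Sections 5.4 and 7.1.1 summarise topics and do not reproduce the form, and the variable list in 10.3 is open-ended. The form may already ask about allergies. This stands: the finding on detection covers only what the protocol describes. Even so, a recorded allergy would have no criterion in 5.2 to act on it.

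**Informal safeguards exist.** Consent involves explaining the agent and its risks, with time for questions (13.3), so a parent may mention an allergy. Families are told to call about any side effect (2.4.1). These narrow the practical gap, but they depend on chance or come after dosing, and they do not make the child ineligible.

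**Allergy is not presented as a likely event.** Section 2.4.1 calls serious effects rare, 8.1 anticipates only minimal effects, and 10.6.3 says serious effects are not expected. This stands. Allergic reaction is the protocol's example of a rare event, and a reader should not infer that the protocol expects it.

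**Stronger consequences might be inferred.** A reader might suppose that any reaction breaks a child's blind, or that three reactions stop the trial, and might express that as 3/27 = 11.1% of the retapamulin arm. The documents do not support this. Section 10.6.3 requires a serious adverse event. Section 8.6 requires three grade 3 events judged probably related; it counts events and does not restrict them to one arm. With one event per child, the enrolled denominator would give 3/54 = 5.6%. Neither percentage measures how many children have a known allergy.

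**Conclusion.** The omission is real. As written, 5.2 leaves a child with a known earlier reaction to a study ointment eligible, and no step described before dispensing at Visit 1 would identify that child. It is a gap between the eligibility and risk sections that bears on participant safety.

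Its size cannot be computed. The documents give no allergy frequency or extent of prior use, and the number affected is probably small. The endpoint, sample size and analysis plan need no change.

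The conclusion on eligibility rests on the text of 5.1 and 5.2 alone. The conclusion on detection assumes that the unseen questionnaire asks no more than the protocol describes. If it does ask about allergies, only the missing link to eligibility remains.

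**What to change.** 1. Reconcile 5.2 with 2.4.1, 8.1, 8.6, 10.6.3 and the attached package insert, so that the protocol states how known hypersensitivity to a component of either ointment is handled at entry. The investigator and the research pharmacy should set the wording. Check that the no-precautions statement in 7.5.1 agrees with the result.
2. Confirm that the initial questionnaire asks about allergies. If it does not, add one question, answered before randomisation at Visit 1.

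**Cost.** The change to 5.2 can go into the next amendment, with IRB approval under 13.2. By section 19, changing the questionnaire needs no protocol amendment, although 13.2 has participant materials submitted to the IRB. The effect on recruitment should be negligible.
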